4.3 Recruitment Strategy and Patient Screening

All patients presenting to participating surgeons between the ages of 18 to 60 years with a femoral neck fracture will be screened. Potentially eligible patients will be approached to participate in the FAITH-2 trial. All screened patients will be classified as:

1. Excluded (if they subsequently do not meet the eligibility criteria).
2. Missed (eligible but not randomized due to error).
3. Included (eligible and randomized).

4.4 Randomization Methods

Eligible patients will be randomized in equal proportions to one of four treatment groups: 1) cancellous screws with vitamin D₃ supplementation, 2) cancellous screws with placebo supplementation, 3) SHS with vitamin D₃ supplementation, or 4) SHS with placebo supplementation. Allocation will be concealed using a centralized 24-hour computerized randomization system that will allow Internet based allocation. The treatment allocation will be stratified on the following prognostic factors to ensure balance between the intervention groups: 1) undisplaced or displaced femoral neck fractures; 2) presence or absence of an ipsilateral femoral shaft fracture; and 3) geographic region of recruiting centre (industrializing countries versus industrialized countries).

4.5 Surgical Interventions

4.5.1 Multiple Cancellous Screws

Participants allocated to the cancellous screw group will receive multiple threaded screws (with a minimum of 3 screws and a minimum diameter of 6.5 mm) (**Figure 2**). Any threaded screw or hook pin as well as buttress plates will be permitted. The number of screws, screw configuration, reduction technique, implant manufacturer, use of buttress plates, decision to perform a capsulotomy, use of injectable bone substitutes,

use of bone grafts, or aspiration of an intracapsular hematoma will be documented but not prescribed due to lack of evidence favouring any of these approaches.

4.5.2 Sliding Hip Screws

Participants allocated to the SHS group will receive a single larger diameter partially threaded screw affixed to the proximal femur with a sideplate using a minimum of 2 screws for fixation (**Figure 3**). Surgeons will be permitted to use any fixed-angle plate construct which includes a large diameter screw or blade that can slide within the plate. Surgeons will be allowed to use derotational screws and buttress plates. The use of a compression screw, implant manufacturer, reduction technique, decision to perform a capsulotomy, use of injectable bone substitutes, use of bone grafts, and aspiration of intracapsular hematoma will be documented but not prescribed.

4.5.3 Ipsilateral Femoral Shaft Fractures

Ipsilateral femoral shaft fractures will be treated with plating or retrograde nailing. The method of fixation will be documented. We will also document the following outcomes on the shaft fracture: 1) the time to radiographic fracture healing of the ipsilateral femoral shaft; 2) re-operation; and 3) fracture-related complications.

4.5.4 Adherence to Surgical Intervention

Crossovers rates between the SHS and multiple cancellous screw groups are likely to be low because both implants are inserted with similar techniques and surgeon expertise in both techniques is likely to be very similar. Participants will be randomized as close to surgery as possible. Any participants who crossover will be analyzed in the group to which they were allocated, maintaining the intention to treat approach for the analysis.

4.6 Nutritional Supplementation

4.6.1 Administration of Nutritional Supplementation

Nutritional supplementation will be administered upon hospital discharge or within two weeks of the participant's femoral neck surgery, whichever comes first. Ideally, participants should be administered the nutritional supplementation as soon as possible following their surgery. Each participant will be provided with a six-month supply of vitamin D₃ supplementation or placebo.

4.6.2 Vitamin D Supplementation

Participants allocated to the vitamin D Group will receive a bottle of 2,000 IU vitamin D₃ drops (Ddrops®, Ddrops Company). Participants will be instructed to take two drops daily for six months, for a total daily dose of 4,000 IU. All vitamin D₃ supplement bottles will be labeled in a blinded manner according to Health Canada guidelines and Good Manufacturing Practice.

4.6.3 Placebo Supplementation

Participants in the placebo group will receive an identical bottle of placebo drops with no active ingredient. Similarly, they will be instructed to take two drops daily for six months. The placebo supplement is also manufactured by the Ddrops Company. All placebo supplement bottles will be labeled in a blinded manner according to Health Canada guidelines and Good Manufacturing Practice.

4.6.4 Adherence to Nutritional Supplementation

Crossovers are unlikely between the nutritional supplementation groups as participants and surgeons will be blinded to the vitamin D and placebo treatments. Additionally, participants will be explained the importance of treatment compliance at each follow-up visit. Study personnel will be instructed that prescribing study participants vitamin D is prohibited. Participants will also be instructed to not take additional supplements containing vitamin D for the duration of the trial. Previous research has demonstrated a 96% adherence to daily vitamin D self-administration in adults⁴⁰. Additionally, the nutritional treatment arm represents a pragmatic effectiveness comparison, and given the placebo-controlled blinding, there is no reason to suspect differential compliance between the treatment groups will occur. We will document any deviations to the adherence to nutritional supplementation.

4.7 Standardization of Peri-Operative Care

To ensure similar peri-operative regimens participants should receive antibiotic prophylaxis (i.e. cephalosporin, or equivalent coverage) within one hour prior to surgery. Weight bearing status will be determined by the participants' attending surgeon and we will document the participants' weight bearing status at each visit. We will also document surgical delay and whether the participant received physiotherapy.

4.8 Primary and Secondary Outcome Measures

4.8.1 Primary Outcome

The primary outcome will be a composite of patient important outcomes that occur within the 12 months post-surgery follow-up period. Specifically, these are limited to:

1. *Re-operation*: any unplanned surgery related to the treatment of the femoral neck fracture;
2. *Femoral head osteonecrosis*: any evidence of osteonecrosis on any follow-up medical imaging study (i.e., radiographs, magnetic resonance imaging (MRI), or other advanced imaging study);
3. *Severe femoral neck malunion*: fracture healing with femoral neck shortening of >10 mm in any plane on follow-up x-rays;⁹ or
4. *Nonunion*: failure of the fracture to progress towards healing defined as a Radiographic Union Score for Hip (RUSH)^{41,42} score below a pre-determined threshold specific for nonunion at 6 months or greater post-injury.

4.8.2 Secondary Outcome

The secondary outcomes will include:

1. HRQL and patient-reported function as measured by the:
 - Short Form-12 (SF-12)⁴³ which measures self-reported quality of life through an 8-domain profile of functional health and well-being, physical and mental health summary measures and a preference-based health utility index.
 - Hip Outcome Score (HOS)⁴⁴ which measures self-reported functional status through 28 items and two sub-scales that pertain to activities of daily living (ADLs) or higher level activities such as those necessary to participate in sports.
2. Fracture healing complications: These will include wound healing problems, infection (superficial and deep), hardware failure, hardware breakage, painful hardware, and peri-prosthetic fracture.
3. Radiographic fracture healing: The date of healing will be determined by the Central Adjudication Committee (CAC). They will consider a fracture as healed when there is obliteration of the fracture line by newly formed bone along the cortices and within the trabecular bone on anterior-posterior and lateral radiographs.

4.9 Frequency and Duration of Follow-Up

Participants will be followed for a period of 12 months post-surgery (**Figure 4**). Participant follow-up visits will occur at enrollment (baseline), post-operative (24 hours to 14 days window), 6 weeks (2 week to 8 week window), 3 months (2 to 4 month window), 6 months (5 to 7 month window), 9 months (7 to 11 month window), and 12 months (11 months or greater window) post-surgery.

The **Schedule of Assessments (Table 1)** details the requirements and procedures for each visit. All study outcomes (as defined in sections 4.8.1 and 4.8.2) will be documented on the case report forms (CRFs) at each follow-up visit.

Additionally at all follow-up visits the participant will complete the SF-12 and HOS questionnaires. At the post-surgery follow-up visit participants will answer all questionnaires based on their pre-injury status. Questionnaires for subsequent follow-up visits will be answered based on the participant's current status at the time of follow-up.

For participants who have an ipsilateral femoral shaft fracture at each follow-up visit we will document: 1) the time to radiographic fracture healing of the ipsilateral femoral shaft; 2) re-operation; and 3) fracture-related complications including compartment syndrome, wound healing problems, infection (superficial or deep), hardware failure, hardware breakage, malunion, nonunion, and prolonged pain at the fracture site.

Serious adverse events (SAEs) will also be documented at each visit. X-rays of the participant's fractured hip are required at enrollment (baseline), post-surgery, and at, 6

weeks, 3 months, 6 months, 9 months, and 12 months post-surgery. As the primary outcome includes radiographic outcomes, it is important that X-rays be obtained at all follow-up visits. MRI or other advanced imaging studies are not required and may be ordered at the discretion of the attending surgeon. Clinical notes may also be requested. If additional imaging studies are obtained, they will be sent to the Methods Centre for outcome adjudication. In addition, at the 12-month follow-up visit, any re-operations that may be planned for the participant will be documented.

4.10 Participant Retention

Once a patient is enrolled in the trial, the clinical site will make every reasonable effort to follow the participant for the entire duration of the study period. The expected follow-up rate for this study is greater than 90% based on similar fracture trials performed by the study investigators.^{39,45} To maximize participant retention, all possible attempts should be made to collect as much data as possible and to reduce loss to follow-up. We have implemented procedures to improve participant retention (**Figure 5**).⁴⁶ Clinical site personnel are responsible for implementing these procedures, as well as developing their own local procedures, in order to attain this follow-up rate.

Participants may discontinue their participation in the FAITH-2 study at any time. If a participant wishes to withdraw their consent from the study, we will use the following strategies to reduce the demands of the study and help to retain the study participant:

1. Ask them to return for a clinic visit at the 12 month follow-up only and ensure that the items included in the primary outcome (re-operation status and X-ray) are completed.
2. Ask them if research personnel may contact them by telephone to ask about their status.
3. Ask them for permission to access their medical chart to identify information about their status.

We will only deem participants lost to follow-up after all exhaustive measures have been taken to locate the participant. Participants should not be deemed lost to follow-up until the 12 month visit is due and all attempts to contact the participant have been exhausted.

We will not remove participants from the study if the study protocol was not adhered to (e.g. participant received wrong treatment arm, early discontinuation of nutritional supplement, occurrence of protocol deviations, missed follow-up visits, etc.). We will document the reasons for participant withdrawal from the trial (e.g. withdrawal of consent or lost to follow-up).

4.11 Blinding

Surgeons, research personnel, participants, and members of the CAC cannot be blinded to the treatment allocation of the surgical interventions (SHS versus cancellous screws).

The data analyst and the Steering Committee will be blinded to the surgical treatment allocation.

The complete blinding of the nutritional supplement will be achieved by using vitamin D₃ and placebo liquid products that are indistinguishable. This will ensure that the surgeon, participants, research personnel, the CAC members, the data analyst, and the Steering Committee are blinded to the participants' nutritional supplementation allocation. An unblinding procedure will be made available when necessary (**Figure 6**).

5.0 STATISTICAL PLAN

5.1 Sample Size Determination

The choice of sample size is based upon independent comparisons of the SHS versus multiple cancellous screw *AND* vitamin D supplementation versus placebo for the primary outcome (patient important outcomes). This is based on the assumption that both interventions will act independently. We will use an alpha level of 0.5 for the primary outcome and all statistical hypotheses will be 2-sided.

The preliminary sample size calculations are based on the limited published literature. As outlined in section 1.2, a pooled estimate from 18 published studies revealed a combined femoral head osteonecrosis and fracture nonunion incidence of 25%. In addition to femoral head osteonecrosis, the composite primary outcome includes other events such as re-operation and severe femoral neck malunion. These additional complications are expected to increase the composite event rate to approximately 40%; therefore, a conservative event rate of 30% is assumed in the cancellous screw and placebo groups.

The trial is powered for a RRR of 33% for each of the treatment comparisons: SHS versus multiple cancellous screws *AND* vitamin D₃ supplementation versus placebo. This RRR estimate is based on the best available literature and coincides with a 10% absolute risk reduction that was deemed to be clinically significant by over 500 surveyed surgeons.¹⁰ For the surgical comparison, Gardner et al²¹ and Chen et al²² reported an 86% and 100% RRR for reoperation using a SHS. Other more heterogeneous retrospective studies by Liporace et al²³ and Razik et al²⁴ suggest RRRs from SHS between 50-88% for osteonecrosis and 63% for nonunion (Section 1.3). Since these are uncontrolled retrospective studies, a conservative effect size estimate is maintained. With regard to the expected treatment effect of vitamin D supplementation, there are no clinical studies that quantify its efficacy to reduce fracture healing complications. Despite the lack of direct data, vitamin D supplementation following acute fractures has demonstrated a 40% increase in fracture callus density in human participants²⁹ and an 80% increase in mechanical strength in animal model.²⁸ Experimental evidence also suggests benefits of increased fracture area vascularity and improved healing that may also contribute to the treatment effect of vitamin D supplementation. We have also assumed the same RRR of 33% in the vitamin D treatment arm.

Considering a 30% event rate in the cancellous screw and placebo group, a RRR of 33% will give a 20% event rate in the SHS and placebo group. Therefore, the event rate for the total placebo group (combined over cancellous screw and SHS groups) is expected to be 25%. Similarly a RRR of 33% due to vitamin D₃ supplementation will result in a 20% event rate in the cancellous screw and vitamin D₃ supplementation group. This leads to an expected event rate of 25% for the total cancellous screw group (combined over both the placebo and vitamin D₃ supplementation groups). Therefore our sample size calculation is based on a control group event rate of 25% and a RRR of 33%.

We will recruit a sample size of 808 patients with full follow-up. Based on an anticipated 10% loss to follow-up³⁹, 898 patients will need to be enrolled in the FAITH-2 trial. **Table 2** demonstrates that the chosen sample size will have a high likelihood of detecting a RRR of 33% or greater across a plausible range of expected primary outcome events (patient important complication), and moderate power for slightly lower effect sizes. Furthermore, if there are synergistic effects between the surgical and vitamin D interventions, there will be even greater study power.

5.2 Statistical Methods

5.2.1 General

The baseline characteristics will be analyzed using descriptive statistics reported as mean (standard deviation) or median (first quartile, third quartile) for continuous variables depending on the distribution and count (percent) for categorical variables. All outcome analyses will adhere to the intention-to-treat principle. The reporting of the trial will follow the CONSORT criteria (www.consort-statement.org). We will provide estimates of our composite outcome of patient important outcomes using proportions with 95% confidence intervals and associated p-values. All p-values will be reported to three decimal places with those less than 0.001 reported as p<0.001. The criterion for statistical significance will be based on alpha = 0.05. We will use SAS (Cary, NC) to perform all analyses.

5.2.2 Primary Analyses

Two independent comparisons between the treatment groups (SHS versus cancellous screws *AND* vitamin D₃ supplementation versus placebo) will be made using the chi-square statistic and an alpha level of 0.05. **Table 3** shows the details for the analysis of primary outcomes.

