		Relative Risk Reduction from the SHS and vitamin D supplementation					
		20%	25%	30%	33%	35%	40%
Incidence of Patient Important Outcomes in the control groups	20%	2994	1890	1294	1060	936	706
	25%	2266	1434	984	808	714	540
	30%	1782	1130	778	638	566	428
	35%	1436	914	630	518	460	348
	40%	1178	752	520	428	380	288

- Total sample size required to achieve 80% power for the independent comparisons of the SHS versus cancellous screws AND vitamin D supplementation versus placebo.
- Grey highlighted boxes denote scenarios where we have more than 80% power (alpha=0.05, 2-sided) to detect the hypothesized difference, given our proposed sample size of 808.
- Control groups: cancellous screws and placebo supplementation

Table 3: Summary of Primary Outcome Analyses

Variable/Outcome	Hypothesis for Surgical Treatments	Hypothesis for Nutritional Supplementation	Outcome Measures	Method of Analysis
Re-operation	The incidence of re-operation, femoral head osteonecrosis, severe femoral neck malunion, or nonunion will be lower in patients receiving a SHS compared to cancellous screws.	The incidence of re-operation, femoral head osteonecrosis, severe femoral neck malunion, or nonunion will be lower in patients receiving vitamin D versus placebo.	Re-operation anytime within 12 months	Chi-square statistic with independent comparison for the surgical treatments and nutritional treatments (alpha=0.05)
Femoral head osteonecrosis			Evidence of femoral head osteonecrosis on X-Rays or MRI	
Severe malunion			Evidence of severe femoral neck malunion on X-Rays	
Nonunion			Failure of the fracture to progress towards healing defined as a Radiographic Union Score for Hip (RUSH) ^{41,42} score below a pre-determined threshold specific for nonunion at 6 months or greater post-injury	

[figure not shown]
*The primary outcome is a composite of re-operation, femoral head osteonecrosis, severe femoral neck malunion, or nonunion.

Table 4: Summary of Secondary Analyses

Variable/Outcome	Hypothesis for Surgical Treatments	Hypothesis for Nutritional Supplementation	Outcome Measures	Method of Analysis
HRQL and function	HRQL and function will be better in patients receiving SHS versus cancellous screws.	HRQL and function will be better in patients receiving vitamin D versus placebo.	HOS and SF-12	Summary statistics of means and confidence interval Longitudinal modeling to include treatment and time

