8.0 PRIMARY CLINICAL ENDPOINT

The primary analyses will first be completed using only blinded treatment groups. All outcome analyses will be performed using the intention to treat approach. The FAITH-2 study primary clinical endpoint is a composite of patient important outcomes that occur within the 12 months post-surgery follow-up period (**Table 9**). Specifically, these are limited to 1) re-operation, 2) femoral head osteonecrosis, 3) severe femoral neck malunion, and 4) nonunion.

The first analysis of clinical outcomes will be a Cox regression with main effects for implant type and supplementation, and the interaction between the two. If the interaction is not significant at $\alpha=0.05$ we will perform two independent comparisons between the treatment groups (SHS versus cancellous screws AND separately vitamin D₃ supplementation versus placebo) using the chi-square statistic and an alpha level of 0.05 for the composite of patient important outcomes (**Tables 10 and 11**).

If the interaction is significant we will keep this interaction term in all subsequent analyses, and present two hazard ratios (HRs) with 95% confidence intervals (CIs) for the surgical intervention and two HRs for the nutritional supplementation (i.e. We will report an HR for SHS versus cancellous screws in those who receive vitamin D, and a separate HR for SHS versus cancellous screws in those who receive placebo. We will also report an HR for vitamin D versus placebo in those who receive SHS, and a separate HR for vitamin D versus placebo in those who receive cancellous screws) The results will be summarized in **Table 12**. Kaplan-Meier curves will also be constructed.

Table 9: Primary Clinical Endpoint Components and Reasons for Secondary Procedures

Outcome	Definition
Unplanned Secondary Procedures (study event)	
Any unplanned surgery related to the treatment of the femoral neck fracture. Specific unplanned secondary procedures include:
 
 • Implant removal • Bone graft • Wound closure • Proximal femur osteotomy • Implant exchange – THA • Implant exchange – HA • Implant exchange – CS • Implant exchange – SHS • Implant exchange – Other IF • Soft tissue procedure • Dynamization • Osteochondroplasty

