Reasons for Secondary Procedures	
 • Shortening • Nonunion • Femoral head osteonecrosis • Deep infection • Superficial infection • Painful implant • Implant failure/breakage • Hip dislocation • Peri-prosthetic femur fracture • Hip instability • Wound healing problem • Screw penetration • Screw cut-out • Post traumatic arthritis • IT Fracture • Relieve pain
Femoral Head Necrosis	Any evidence of osteonecrosis on any follow-up medical imaging study (i.e., radiographs, magnetic resonance imaging (MRI), or other advanced imaging study)
Severe Femoral Neck Malunion	Fracture healing with femoral neck shortening of >10 mm in any plane on follow-up x-rays ¹
Nonunion	Failure of the fracture to progress towards healing defined as a Radiographic Union Score for Hip (RUSH) ^{2,3} score below a pre-determined threshold specific for nonunion at 6 months or greater post-injury.

Table 10: Primary Clinical Endpoint, According to Surgical Treatment (No Significant Interaction Between Implant Type and Supplementation Present)

End Point	Variable	Overall N=	Surgical Treatment X N=	Surgical Treatment Y N=	P-Value
Primary Clinical Endpoint of Re-operation					
Re-operation	Adjudicated Data				
Procedure for Nonunion Implant removal Bone graft Proximal femur osteotomy Implant exchange – THA Implant exchange – IF	Adjudicated Data				
Procedure for Femoral Head Osteonecrosis Implant removal Implant exchange – THA	Adjudicated Data				
Procedure for Deep Infection Wound closure Implant exchange – SHS Soft tissue procedure	Adjudicated Data				
Procedure for Painful Hardware Implant removal Bone graft Implant exchange – THA	Adjudicated Data				
Procedure for Screw Penetration Implant removal	Adjudicated Data				
Procedure for Post-Traumatic Arthritis Osteochondroplasty	Adjudicated Data				
Procedure for IT Fracture Implant exchange – IF	Adjudicated Data				
Procedure for Relieving Pain Implant exchange – THA	Adjudicated Data				
Femoral head osteonecrosis					
Femoral head osteonecrosis	Adjudicated Data				
Severe femoral neck malunion					
Severe femoral neck malunion	Adjudicated Data				
Nonunion					
Nonunion	Adjudicated Data				

Table 11: Primary Clinical Endpoint, According to Nutritional Supplementation (No Significant Interaction Between Implant Type and Supplementation Present)

End Point	Variable	Overall N=	Nutritional Supplementation X N=	Nutritional Supplementation Y N=	P-Value
Primary Clinical Endpoint of Re-operation					

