Re-operation	Adjudicated Data				
Procedure for Nonunion Implant removal Bone graft Proximal femur osteotomy Implant exchange – THA Implant exchange – IF	Adjudicated Data				
Procedure for Femoral Head Osteonecrosis Implant removal Implant exchange – THA	Adjudicated Data				
Procedure for Deep Infection Wound closure Implant exchange – SHS Soft tissue procedure	Adjudicated Data				
Procedure for Painful Hardware Implant removal Bone graft Implant exchange – THA	Adjudicated Data				
Procedure for Screw Penetration Implant removal	Adjudicated Data				
Procedure for Post-Traumatic Arthritis Osteochondroplasty	Adjudicated Data				
Procedure for IT Fracture Implant exchange – IF	Adjudicated Data				
Procedure for Relieving Pain Implant exchange – THA	Adjudicated Data				
Femoral head osteonecrosis					
Femoral head osteonecrosis	Adjudicated Data				
Severe femoral neck malunion					
Severe femoral neck malunion	Adjudicated Data				
Nonunion					
Nonunion	Adjudicated Data				

Table 12: Primary Clinical Endpoint (Significant Interaction Between Implant Type and Supplementation Present)

End Point	Variable	Overall N=	Surgical Treatment X N=	Surgical Treatment Y N=	Nutritional Supplementation X N=	Nutritional Supplementation Y N=	Hazard Ratio (95% CI)				P- Value
							Surgery X + Supplement X vs. Surgery Y + Supplement X	Surgery X + Supplement Y vs. Surgery Y + Supplement Y	Surgery X + Supplement X vs. Surgery X + Supplement Y	Surgery Y + Supplement X vs. Surgery Y + Supplement Y	
Primary Clinical Endpoint: re-operation, femoral head osteonecrosis, severe femoral neck malunion, nonunion	Adjudicated Data										
Primary Clinical Endpoint Components											
Malunion Implant removal Bone graft Wound closure Proximal femur osteotomy Implant exchange – THA Implant exchange – HA Implant exchange – IF (crossover) Implant exchange – IF (original) Implant exchange – Intramedullary nailing Implant exchange – curved plate and IF Implant exchange – 110 degree blade plate Soft tissue procedure Dynamization Osteochondroplasty	Adjudicated Data										
Nonunion Implant removal	Adjudicated Data										

Bone graft Wound closure Proximal femur osteotomy Implant exchange – THA Implant exchange – HA Implant exchange – IF (crossover) Implant exchange – IF (original) Implant exchange – Intramedullary nailing Implant exchange – curved plate and IF Implant exchange – 110 degree blade plate Soft tissue procedure Dynamization Osteochondroplasty											

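### The primary chi-square leaves out the three randomisation factors; a stratified comparison with a risk difference and confidence interval would be a small, low-cost improvement

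*Combined protocol and SAP*

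**What the plan says.** Protocol 5.2.2 states that the two marginal comparisons "will be made using the chi-square statistic and an alpha level of 0.05". Protocol Table 3 lists the same test "with independent comparison for the surgical treatments and nutritional treatments (alpha=0.05"). SAP 8.0 puts a step in front of it: "a Cox regression with main effects for implant type and supplementation, and the interaction between the two". If that interaction is not significant, the SAP compares each margin "using the chi-square statistic and an alpha level of 0.05 for the composite of patient important outcomes". No strata or covariates are mentioned in any of these places.

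Protocol 4.4 says: "The treatment allocation will be stratified on the following prognostic factors to ensure balance between the intervention groups". The factors are displacement, ipsilateral femoral shaft fracture and region (industrialising or industrialised), giving eight strata. Of these, only displacement reappears in an outcome model, and only in the subgroup analyses (protocol 5.2.4 and Table 5, SAP 11.0).

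On estimation, SAP 8.0 names hazard ratios with 95% CIs if the interaction is significant. Table 12, which serves that case, has a composite row: "Primary Clinical Endpoint: re-operation, femoral head osteonecrosis, severe femoral neck malunion, nonunion". If the interaction is not significant, no between-group measure is named and the result goes to Tables 10 and 11. Their primary block is headed "Primary Clinical Endpoint of Re-operation". They have rows for the four components but none for the composite, and no column for an effect or its CI. Protocol 5.2.1 does promise composite proportions with 95% CIs and p-values. SAP 10.0 says missing data will be multiply imputed.

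**The concern.** When allocation is balanced within strata that predict outcome, part of the outcome variation is the same in both arms by design. The plain chi-square still counts that variation as noise, so its standard error is somewhat too large. The three factors are known for every patient at randomisation, so a stratified analysis needs no new data.

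The second matter is what the reader gets from the analysis. The sample size assumes that the two interventions act independently, so the no-interaction branch is the expected one. There the SAP names a p-value only. Protocol 5.1 refers to "a 10% absolute risk reduction that was deemed to be clinically significant by over 500 surveyed surgeons", and a p-value cannot show whether the data include or exclude a difference of that size.

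**Working it through.** **Inputs from the documents.** Control margin 25% and RRR 33%, so 25% v 16.75% (protocol 5.1). Two-sided alpha 0.05 and 80% power (protocol Table 2; section 5.1 prints alpha as 0.5, but every other place has 0.05). Equal allocation to four cells (4.4). 80% of fractures displaced (1.2).

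**The plan's own figure.** Mean rate 0.20875, difference d = 0.0825.
- Uncorrected: n = [1.96·√(2·0.20875·0.79125) + 0.8416·√(0.25·0.75 + 0.1675·0.8325)]² / 0.0825² = 380 per margin arm.
- Continuity-corrected: (n/4)·[1 + √(1 + 4/(n·d))]² = 404 per arm, total 808. 808/0.9 = 898. Both match.
- An uncorrected chi-square at 404 per arm has about 82.4% power, so there is a little slack before any change.

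**Effect of stratifying at N=808.** The documents give no outcome rates by stratum and no block method, so the following are assumptions: 10% shaft fracture, 50/50 region, permuted blocks of 4 within strata, and the odds ratios shown. Cell rates are calibrated to 30% in the cancellous/placebo cell with a risk ratio of 0.67 per treatment (null: 25% in all cells). There were 40,000 trials per setting.

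| Odds ratios: displacement / shaft / region | Type I, chi-square | Type I, stratified | Power, chi-square | Power change |
|---|---|---|---|---|
| 1 / 1 / 1 | 5.0% | 5.0% | 82.7% | −0.1 |
| 2 / 1.5 / 1.5 | 4.7% | 4.9% | 82.7% | +0.5 |
| 3 / 2 / 2 | 4.3% | 4.8% | 83.4% | +1.0 |
| 6 / 3 / 3 | 3.7% | 5.0% | 83.9% | +1.9 |

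Analytic check: chi-square type I error = 2·[1 − Φ(1.96·√v)], where v is total variance over within-stratum variance. For v = 1.00, 1.02, 1.06 and 1.13 this gives 5.0%, 4.8%, 4.4% and 3.7%.

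The 95% CI half-width for the risk difference is 5.57 points unadjusted, against 5.53, 5.47 and 5.35 stratified in the last three rows.

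A second set of assumptions (15% shaft fracture, odds ratios from 1.5/1.25/1.25 to 6/3/2, 100,000 trials per scenario) gave chi-square type I error of 5.0% down to 4.1%, and power gains of about 0.1 to 2.0 points.

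**At N=86**, the count printed in the SAP Table 2 shell (about 18 events at the mean rate: 86 × 0.20875). Power is about 14% to 16%, and stratifying changes it by −0.5, −0.1, +0.2 and +1.2 points across the four rows. On average 1.4 patients fall in a stratum with only one arm and contribute nothing. Type I error of the stratified test is 4.8% to 5.1%. The test and the risk difference could be computed in all 320,000 simulated trials, and the risk ratio in all but 76 (76/320,000 = 0.02%).

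**What the estimate would show.**
- At the design rates: 8.25 ± 1.96·√(0.25·0.75/404 + 0.1675·0.8325/404) = 8.25 ± 5.58 points, so 2.7 to 13.8. The risk ratio is 0.67 (0.51 to 0.88).
- For 25% v 20%: 5.0 ± 5.75 points, so −0.7 to 10.7, with chi-square p = 0.089. That result is non-significant, yet compatible with zero, with the planned 8.25-point contrast and with the surgeons' 10 points.

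**The case against.** The strongest reply is that nothing here is broken. The chi-square is valid, the three places that specify it agree, and no section promises adjustment. Protocol 4.4 gives balance as its reason for stratifying. The largest gain needs odds ratios of 6/3/3, for which the documents offer no evidence; the moderate case gives half a point of power. All of this stands and limits the size of the point. It does not remove it, because the protocol itself calls the factors prognostic and using them needs no new data.

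The missing effect measure is also mostly a matter of completing the SAP. Protocol 5.2.1 promises composite proportions with CIs, both documents commit to CONSORT reporting, and a difference can be worked out from arm counts. A reader might infer from Tables 10 and 11 that the composite will go unanalysed. The documents do not support that: the text of SAP 8.0 explicitly tests the composite, so the heading and missing row are drafting slips in shells.

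A reader might also want the Cox interaction model stratified. No benefit was shown. In a small check at N=808 (300 trials per setting), power against an assumed interaction was 67% unstratified v 69% stratified in one setting and 71% v 71% in another. The simulation error is about 2.7 points (√(0.68·0.32/300)).

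Finally, the 10-point figure should not be read as the target of the marginal test. It corresponds to 30% v 20% within a single cell contrast; the planned marginal contrast is 25% − 16.75% = 8.25 points.

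**Conclusion.** The point holds as a minor improvement in efficiency and reporting. Ignoring the strata makes the primary test mildly conservative, with type I error of about 3.7% to 5.0%, and gives up about 0 to 2 points of power at N=808 and little or nothing at N=86. These ranges rest on assumed odds ratios, shaft-fracture and region proportions, and balanced allocation within strata. If the factors do not predict outcome, nothing is gained.

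A reader might infer that the primary analysis is invalid, produces excess false positives or leaves the trial underpowered. None of these follows: the error is in the conservative direction, 808 reproduces, and the planned power is met without adjustment. The more useful gain is that the stratified method brings a named between-group estimate and CI into the branch where the SAP names none.

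**What to change.** - In protocol 5.2.2, protocol Table 3 and SAP 8.0, make each marginal primary comparison a Cochran-Mantel-Haenszel test stratified by the three randomisation factors as recorded at randomisation. Report a Mantel-Haenszel risk difference and risk ratio with 95% CIs.
- State how results are pooled over the imputations in SAP 10.0. The risk difference and log risk ratio can be combined by Rubin's rules; the rule for the test statistic should also be written down.
- Keep the unadjusted chi-square as a sensitivity analysis and as the only fallback if the stratified analysis cannot be computed.
- Read the risk difference CI against both the planned 8.25 points and the surgeons' 10 points.
- As a consequential tidy-up, add a first row for the four-part composite to SAP Tables 10 and 11, with this estimate and its CI, and correct the re-operation heading.
- Leave the Cox interaction model as it is.

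The cost is text in three places, which may need a formal amendment under protocol 7.5, and two table shells. No new data or patients are needed. The drawback is that a few patients in one-arm strata drop out of the comparison if enrolment is small.
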